A. Participants: U.S. Somali Refugee Community Sample

We will conduct this study in Seattle, WA, and Columbus, OH. The study will be a small RCT ($N = 60$) comparing Islamic Trauma Healing to waitlist (WL) (1:1 randomization, using cluster randomization of one to three individuals), with a three-month follow-up.

Inclusion and Exclusion Criteria. Men and women with trauma exposure and trauma-related avoidance or reexperiencing will participate in the study. Inclusion and exclusion criteria were carefully selected to help individuals self-identify as needing the program while also not conducting formal diagnostic measures that could stigmatize or alienate potential group members. Specifically, if the groups become known as groups for "patients" or for the "insane," many individuals in need of help will not participate. Concrete, behaviorally obvious inclusion criteria were chosen to facilitate lay leader and self-referral. DSM-5 definition of trauma exposure allows for a variety of events including witnessing or experiencing "life threatening events." Two behavioral symptoms of PTSD were chosen, specifically avoidance and re-experiencing symptoms, that are common, readily recognized, often easily linked to trauma exposure; and accordingly, easy for individuals to identify.

Potential participants will self-identify as needing trauma healing. We chose not to use formal PTSD and depression interview diagnostic measures for several reasons. Somali refugees may not identify or report many of the symptoms associated with a Western conceptualization of PTSD and depression (Bentley et al., 2011). Further, in line with dimensional models of psychopathology, subthreshold PTSD symptoms are also common, often unremitting, and impairing and also warrant intervention (Bergman et al., 2016). By not requiring a DSM-5 diagnosis of PTSD, a broader conceptualization of post-trauma reactions and associated phenotypes is in line with RDoC Negative Valence Systems and a better match with current thought on the wide range of long-term psychopathology following trauma exposure (Kozak & Cuthbert, 2016, Broman-Fulks et al., 2006).

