Islahul Qulub: Islamic Trauma Healing. Several years of iterative, collaborative development work with the Somali community have guided the content and format of the Islamic Trauma Healing program. A manual for the program was developed (Lang, Zoellner, Graham, Marks, & Feeny, 2016), and a local Imam carefully reviewed the content of the manual. Focus group feedback from lay leaders and group members was also utilized in revisions. The program was designed for groups of 5-7 members, with two lay leaders of the same gender. The program is structured so that the lay leader training, comprised of two 4-hour trainings, focuses on teaching lay leaders the skills of discussion leading, with the manual content providing more of the direct therapeutic work. That is, the lay leaders are not explicitly taught how to be psychotherapists or how to do cognitive behavioral therapy specifically. The manual contains an introduction to trauma healing, including a description of types of trauma exposure and common reactions, as well as Islamic principles related to trauma healing. Session-by-session content is clearly spelled out in the manual. Each session includes time for community building rituals (e.g., sharing tea or coffee), spiritual preparation using a brief supplication written by the local Imam, prophet narratives relevant to trauma healing, and a brief closing supplication also written by the Imam. In the first session, a rationale for the program, common reactions to trauma, and a breathing relaxation exercise are described. Starting in the second session and continuing through the last session, talking individually to Allah about the trauma is conducted. In the last session, group members are encouraged to organize a closing event at which certificates of program completion are given.

The program is 6 sessions long. This duration is in line with evidence that very brief or shortened protocols (e.g., four 30 min sessions) can substantially reduce PTSD symptoms (Cicrang et al., 2011; van Minnen & Foa, 2006). Key components of the program are prophet narratives aimed at targeting trauma-

related beliefs, and talking to Allah, aimed at targeting trauma memories.

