F. Power Analysis

We estimated sample size based primarily on Specific Aim 1. We estimated power to detect effects using G*Power and Optimal Design (for multilevel data), with $\alpha = .05$ and power $(1 - \beta) = .80$, completing 10,000 replications per analysis. With a conservative estimated dropout of 20% across conditions, though no dropout occurred in our pilot work, we will have power to detect moderate to large effects of condition on outcomes at post-treatment ($d = 0.72$) with 30 per group, and ($f^2 = 0.28$) with generalized linear models (GLM),

both large effects. For repeated measures analyses, with 4 data points, 30 per group with 20% missing data, we will be able to detect medium effects ($d = 0.60$) on change over time. These effect sizes are well below the observed effects in our pilot work ($g = 0.76$ to $g = 3.22$). For Specific Aim 2, the same power calculations for Aim 1 apply; however, tests of indirect effects are exploratory, we will be powered to detect a moderate indirect effect ($a*b = 0.25$), using the same constraints as above. To balance feasibility and ability to detect meaningful effects, we will recruit 30 individuals per treatment group

G. Analytic Strategy

Data will be screened for accuracy, missing values, and fit between the data and the assumptions of the general linear and linear mixed-model analysis (e.g., linearity, multivariate normality, independence of errors; Tabachnick & Fidell, 2007). Data transformations or model respecifications will be performed for any violated assumptions. We will implement pattern-mixture models to examine whether the missingness can be considered ignorable. For non-ignorable missing data, values will be multiply imputed and data recombined using Rubin's rules (Rubin, 1987) in the mixed model program. We will examine associations between primary dependent variables and factors such as gender, age, time since trauma, etc. and make appropriate analytic adjustments. We will test all covariate by predictor interactions to ensure our main effects are independent of the level of these putative covariates; these tests of effect modification are easily accommodated. However, we are underpowered to assess these interactions. To account for subjects being nested within groups in the treatment condition, we will co-vary treatment group using dummy codes in all analyses, as linear mixed models are difficult to estimate when the number of clusters is very small (Snijders, 2005).

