Specific Aim 1: Therapeutic Effects

Hypothesis: Those in Islamic Trauma Healing will show a greater reduction of PTSD symptoms and related psychopathology than those in the waitlist condition (WL).

Predictor Variables: Predictor is treatment (Islamic Trauma Healing vs. WL)

Dependent Variables: PTSD severity (PS-SR-5, primary outcome), depression (PHQ-9), somatic symptoms (PHQ-15), and well-being (WHO-5) will be measured.

Analyses: Because of the presence of clustering (participants in groups, observations over time, and participants in random assignment clusters), we will use generalized linear mixed models (GLMMs), which can account for the presence of clustering in data with varying distributional forms. We will compare pre-post GLMMs with those using data from all four time points to estimate the effects of treatment on both the level of the outcome at post-treatment, as well as change over time. To account for clustering (in treatment groups and random assignment clusters), we will include random intercepts for both treatment group and cluster (for those choosing to be randomized in a cluster). Because the waitlist control and non-clustered individuals will *not* be in a cluster, we will use the method outline by Sterba and Bauer (2008) to model random intercepts for *only* those in treatment or a cluster, and test whether modeling residuals as a function of clustering status appropriately models heteroskedasticity of residuals across clustering status. To test models of change over time, these models would be extended to three level models, with random intercepts and random coefficients for time-varying covariates (e.g., time) specified at Level 2 if the model fit is better than a fixed effects model.

Dropout. We will compare the percent of those who drop out of Islamic Trauma Healing to WL using a chi-square test. Reasons for dropout will be documented and compared across groups. Psychopathology and functioning of dropouts will be compared, using chi-square or *t*-tests, as appropriate.

Satisfaction. Means and standard deviation of satisfaction (CSQ) will be reported. A comparison to WL does not make sense, as there are no services with which to compare.

Specific Aim 2: Potential Mediators Change with Active Intervention

Hypothesis: Those in Islamic Trauma Healing will show a greater reduction of negative beliefs (PTCI), connectedness (SC; DSES), and/or forgiveness (TRIM-R) than those in the waitlist condition (WL).

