Predictor Variables: Predictor is treatment (Islamic Trauma Healing vs. WL)

Dependent Variables: Negative beliefs (PTCI), connectedness (SC; DSES), and forgiveness (TRIM-R) will be measured.

Analyses: We will conduct similar analyses to Aim 1, using both GLMs and GLMMs to obtain effect size estimates. In the GLMs, treatment will predict negative beliefs, connectedness, and forgiveness from baseline to post-treatment (controlling for baseline levels). GLMMs will be conducted as above, and treatment will be used to predict post-treatment levels and change over time in the dependent variables, to estimate how groups

STUDY PROTOCOL: A Lay-Led Intervention for War and Refugee Related Trauma: NCT03502278
July 18, 2018

differ in their rate of symptom reduction over the course of treatment.

Exploratory Hypothesis. Changes in negative beliefs (PTCI), connectedness (SC; DSES), and/or forgiveness (TRIM-R) will mediate the relationship between treatment condition and changes in PTSD and related symptoms. For the GLMs, we will predict Session 3 mediators from treatment (a path) and follow-up outcomes from the mediator (b path) controlling for treatment and baseline levels. Mediation will be tested using the product of coefficients method with bootstrapped standard errors (MacKinnon et al., 2009). In the GLMMs, we will conduct a 2-1-1 mediation, predicting the mediator at all time points from treatment (2-1), and the outcome at all time points from the mediator (1-1), controlling for treatment. This will be based on Bauer et al. (2006), generally following the product of coefficients method. It is recognized that this is underpowered.

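### Neither of the plan's two conflicting methods for therapy-group clustering reaches change over time, so the treatment-by-time tests are anti-conservative if groups differ in improvement

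*Combined protocol and SAP*

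**What the plan says.** Section G (Analytic Strategy) gives two rules for participants who share a therapy group.

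- The opening paragraph adjusts for group membership with dummy variables in every analysis, because mixed models are hard to fit with very few clusters. No product of dummy and time is mentioned.
- Specific Aim 1, Analyses, uses mixed models instead: "we will include random intercepts for both treatment group and cluster", restricted to those who are actually in a group or cluster. For change over time the models become three-level, "with random intercepts and random coefficients for time-varying covariates (e.g., time) specified at Level 2", and the time coefficients are kept only if fit improves.

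Level 2 here is the participant. The mediation analysis under Specific Aim 2 is labelled 2-1-1, with treatment at Level 2 and time points at Level 1, which puts the therapy group at Level 3. No time coefficient is given at that level.

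Specific Aim 2 inherits the same models: "GLMMs will be conducted as above, and treatment will be used to predict post-treatment levels and change over time".

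On group size, section B (Materials) says: "The program was designed for groups of 5-7 members". Section D (Procedures) takes the first questionnaire before Session 1.

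**The concern.** The Aim 1 hypothesis is a greater reduction in symptoms, and Aim 2 compares rates of reduction. Both are statements about change. A group, its lay leaders and its dynamics can affect how much members improve, and that is a group-by-time effect. A group intercept, fixed or random, takes the same value at every visit, including the one before the group has met, so it cannot represent such an effect.

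Differences between groups are plausible here. Leaders are volunteers, later leaders are trained by earlier ones, and supervision is set up to catch departures from the manual (sections D and E). If such differences exist, the standard error for treatment-by-time is too small and the interval too narrow, although the plan presents clustering as dealt with.

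**Working it through.** **Inputs from the documents.** 30 per arm (section F); 20% dropout, leaving 24 per arm; four time points; groups of 5-7. Since 30/7 = 4.3 and 30/5 = 6, the active arm has about 4-6 groups. The nominal alpha is .05; I take it as two-sided, which is not stated. No ICC of level or of change appears.

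**The plan's own figures.** The normal formula d = (1.96 + 0.842)·√(2/n) gives 0.723 at n = 30 and 0.809 at n = 24, so the stated 0.72 matches a two-sided test with no dropout. The stated d = 0.60 for change cannot be reproduced uniquely. At n = 24 it needs a variance factor of (0.60/0.809)² = 0.55, which depends on a within-person correlation that is not given. Neither figure shows an allowance for group variation in change.

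**Step 1: the intercept cancels.** Write a group member's outcome as y(t) = fixed part + u + person terms + error, with u the group intercept. Then y(post) − y(pre) contains u − u = 0, and a fitted slope over complete visits is likewise free of u. For illustration take five groups of 5, 24 on waitlist, visits coded 0-3 (sum of squares 5), person-slope variance 0.15 and residual variance 0.4:

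- Variance of one person's slope: 0.15 + 0.4/5 = 0.23.
- Variance of the arm difference: 0.23·(1/25 + 1/24) = 0.01878, so SE = 0.137. The group intercept variance does not appear, so the SE is the same whatever its value.
- If groups differ in slope with variance 0.01, the variance gains 0.01/5 = 0.002 and the SE becomes 0.144.

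These are SEs at known variances. A fitted model without the group slope would push part of that 0.002 into the person slope, so the ratio of the two overstates the gap it would show. Step 2 allows for this.

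**Step 2: size.** Let ρ be the share of the variance of change lying between therapy groups, and m the group size. Ignoring groups gives a variance proportional to 1 + 1 = 2 over the two arms. The true value is 1 + (m−1)ρ for the active arm plus 1 for the waitlist. The ratio is 1 + (m−1)ρ/2, and

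type I error = 2·[1 − Φ(1.96/√(1 + (m−1)ρ/2))].

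Example: m = 6, ρ = 0.10 gives ratio 1.25, 1.96/1.118 = 1.753, error 8.0%.

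| ρ (assumed) | m = 5 | m = 6 | m = 7 |
|---|---|---|---|
| 0 | 5.0% | 5.0% | 5.0% |
| 0.01 | 5.2% | 5.3% | 5.4% |
| 0.05 | 6.2% | 6.5% | 6.8% |
| 0.10 | 7.4% | 8.0% | 8.6% |
| 0.20 | 9.8% | 11.0% | 12.1% |

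**Step 3: simulation.** Change scores (100,000 runs per setting, m = 6, 30 per arm) gave 5.4, 6.4, 8.0 and 11.2% at ρ = 0.01, 0.05, 0.10 and 0.20. REML fits of the four-visit model with a group random intercept and a participant slope (1,500 runs each, Monte Carlo error 0.6-0.7 points) gave 5.7, 7.1 and 7.8% at ρ = 0, 0.05 and 0.10. Replacing the random intercept with main-effect group dummies gave the same three rates, so the section G rule does not repair the problem.

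**Step 4: with group variation in change included.** Analysing group means of change in the active arm, with Satterthwaite degrees of freedom, gave 5.0-5.8% for ρ from 0 to 0.20 and 4-6 groups.

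**The case against.** The strongest reply is that the size is unknown. Nothing in the documents fixes the ICC of change; at 0.05 or below the excess is under two percentage points, and at zero there is none. That stands. A reader might infer that the plan's type I error simply is 7-12%, but that range needs an ICC of about 0.07-0.24 with groups of 6, which the documents neither state nor imply.

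A reader might also infer that clustering enters only as a random intercept, or that every Aim 1 result is affected. The documents support neither. Section G also prescribes dummy codes, which do not help with change but are a second, conflicting rule. Aim 1 also targets the post-treatment level, and a baseline-adjusted model of that level with a group random intercept does carry group differences at that time point.

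The plan promises to screen for independence of errors and to respecify models where assumptions fail. That leaves room for correction but names no group-by-time term, and so few groups give little power to detect the need for one. Finally, this is a small trial meant to inform a larger one and to yield effect sizes. That lowers the stakes of a single p-value, but intervals that are too narrow would mislead the later trial too.

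**Conclusion.** The point holds as a structural gap: neither clustering method in section G puts therapy group into change, and the two methods contradict each other. The cancellation is algebraic for complete data and needs no ICC.

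The consequence is conditional. For groups of 5-7, type I error of the treatment-by-time test is about 5% at an ICC of change of 0, 6-7% at 0.05, 7-9% at 0.10 and 10-12% at 0.20. This affects the change-over-time tests in Aims 1 and 2, and any pre-post model fitted with two rows per person. The figures assume a two-sided test, complete data, equal group sizes and equal total variance of change in both arms, and they ignore the randomisation units of one to three people.

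**What to change.** - Reconcile the opening of section G with Specific Aim 1, so that one method for therapy groups applies throughout.
- In every model of change, add a random coefficient for therapy group, active arm only, on time coded 0 at Session 1. In the pre-post model, put it on a post-baseline indicator. Add the analogous term for randomisation clusters where it can be estimated.
- Keep the existing intercepts unless they estimate at zero or prevent convergence. Randomisation units exist before baseline, and groups may already differ then. Retain the therapy-group time term regardless of fit.
- Test treatment-by-time with Satterthwaite or Kenward-Roger degrees of freedom for outcomes modelled as normal, and a comparable small-sample correction otherwise. This matters: in a REML check of 600 runs, a group slope with a normal reference gave about 5-6% when groups held 0-20% of slope variance, but 9% at 40%.
- Name the group-mean change analysis with Satterthwaite degrees of freedom as the fallback. The error rates in step 4 belong to this analysis, not to the mixed model.
- State the ICC of change assumed for planning.

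The work is SAP wording and a few lines of code. The statistical cost is a wider interval. For five groups of 6 at ρ = 0.10, the group-mean analysis has (1.5 + 1)²/(1.5²/4 + 1²/29) = 10.5 degrees of freedom. The critical value is then about 2.21 instead of 1.96, and the interval is 1.118 × 2.21/1.96 = 1.26 times as wide as one that ignores groups. Over ICCs of 0.05-0.20, the typical (median) estimated degrees of freedom are about 10-13 for five groups and 7-10 for four. The same formula at the true variances gives slightly fewer.

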Male and female lay leaders will be selected based on being a community leader, having a heart for healing and reconciliation in the Somali community, and willingness to later train additional group leaders. Lay leaders will be able to speak and read in both Somali and English. All lay leaders will sign contracts to be individual investigators affiliated with their respective universities. Lay leaders will attend two, 4-hour training sessions (approximately 6 hours actual training, allowing time for arrival and prayer times), where they will receive the manual and an overview of the program, review and practice components of group sessions, and identify potential issues and problem solve. Lay leaders will be volunteers.

Group participants will be recruited through flyers and word of mouth by the lay leaders, community and faith leaders, and self-referral, focusing on those in need of trauma healing based on their report of re-experiencing and/or avoidance of traumatic events. All participants will sign informed consent forms, in either Somali or English depending on their language preference. Randomization to active or waitlist will be conducted using a 1:1 ratio, allowing for individuals or clusters of up to three individuals being randomized as a unit. Questionnaires will be completed prior to the start of group (Session 1), middle (Session 3), and end (Session 6), with a three-month follow up for individuals in the RCT using a Qualtrics link. Participants will receive fifty dollars at the three-month follow up. Groups will meet weekly for 2 hours, with length of time varying depending on breaks for prayer. After each group, lay leaders will meet briefly with a clinical supervisor from the investigational team, either in person or on phone/online, for a discussion of the session, consultation on content or clinical issues that arose during session, and any supervisory notes. Once the six weekly sessions have been completed, a group social event will be held as a closure ceremony and to facilitate community reconciliation. The content of each group session is clearly delineated in the Islamic Trauma Healing manual.

E. Quality Control

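### Dropout is compared with an ordinary chi-square test on individuals although people may be randomised in units of up to three; if unit members tend to leave together, the test overstates the evidence

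*Combined protocol and SAP*

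**What the plan says.** Section A of the combined protocol and SAP describes the design as "1:1 randomization, using cluster randomization of one to three individuals". Section D repeats it: "allowing for individuals or clusters of up to three individuals being randomized as a unit". Section F sets the size: "we will recruit 30 individuals per treatment group".

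Under Specific Aim 1, the Analyses paragraph names random-assignment clusters as a source of dependence. It gives the symptom models a random intercept for treatment group and another for randomisation cluster. The Dropout paragraph of the same Aim then says: "We will compare the percent of those who drop out of Islamic Trauma Healing to WL using a chi-square test". It names no adjustment for units and no exact version of the test.

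Section F gives the only guide to how much dropout to expect: "With a conservative estimated dropout of 20% across conditions, though no dropout occurred in our pilot work".

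**The concern.** A chi-square test on a two-by-two table of people assumes that each person was allocated, and stays or leaves, independently of the others. Allocation is not independent here by design: a pair or trio goes to one arm together. If its members also tend to leave together, their exits carry less information than the same number of unrelated exits. The test does not know this, so its p-values come out too small, whichever arm loses more people.

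The plan recognises this dependence for its symptom outcomes and omits it for dropout. At stake is the only between-arm test of retention in the plan. A chance imbalance of two units could be reported as a real difference in how well the programme keeps people, and carried into the larger study that the Measures section anticipates.

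**Working it through.** **Inputs from the documents.** 60 people, 30 per arm, 1:1, units of one to three (sections A, D, F). Planning dropout is 20%, i.e. 12 of 60, against none in the pilot (section F). The plan gives no power or error figure for the dropout test, so there is none to reproduce; its detectable effect of d = 0.72 concerns symptom outcomes and is not used here.

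**Assumed, because not stated.** The mix of unit sizes (all singles to all trios) and the within-unit correlation of dropout, ρ (main range 0.2–0.6).

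**Step 1: what the stated test returns.** For a leavers in one arm of 30 and none in the other, Pearson's statistic reduces to X² = 60a/(60 − a).

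| Leavers | X² | Chi-square p | Fisher p |
|---|---|---|---|
| 3 v 0 (one trio) | 180/57 = 3.16 | 0.076 | 0.237 |
| 4 v 0 (two pairs) | 240/56 = 4.29 | 0.038 | 0.11 |
| 5 v 0 (trio and pair) | 300/55 = 5.45 | 0.020 | 0.052 |
| 6 v 0 (two trios) | 360/54 = 6.67 | 0.0098 | 0.024 |

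A trio can also tip a result when added to other dropout: 9/30 v 3/30 gives p = 0.053, and 12/30 v 3/30 gives p = 0.007.

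**Step 2: the same events counted in units.** With 30 units, 15 per arm, the chance that two given units fall in the same arm is 2 × (15 × 14)/(30 × 29) = 420/870 = 0.483. With 20 trios, 10 per arm, it is 2 × (10 × 9)/(20 × 19) = 180/380 = 0.474. Two whole units leaving the same arm is therefore close to a coin toss, while the stated test puts it below 0.05.

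**Step 3: type I error.** An approximation uses the design effect D = 1 + (Σm²/Σm − 1)ρ, where m is unit size. The true error of a nominal 5% test is then about 2[1 − Φ(1.96/√D)]. For example, with ten units of each size Σm²/Σm = (10 + 40 + 90)/60 = 2.33. At ρ = 0.6, D = 1.80, 1.96/√1.80 = 1.46, and the error is 14.4%.

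| Mix among 60 people | Σm²/Σm | D at ρ = 0.2 / 0.6 | Approximate error | Simulated, 10–20% dropout, ρ 0.2–0.6 |
|---|---|---|---|---|
| All singles | 1.00 | 1.00 / 1.00 | 5% / 5% | about 5% |
| Six pairs, 48 singles | 1.20 | 1.04 / 1.12 | 5.5% / 6.4% | about 5–8% |
| Ten each of size 1, 2, 3 | 2.33 | 1.27 / 1.80 | 8.2% / 14.4% | 7–15% |
| Twenty trios | 3.00 | 1.40 / 2.20 | 9.8% / 18.6% | 9–20% |

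Formula and simulation agree. At ρ = 0 there is no inflation in any mix.

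**Step 4: would Fisher's test be enough?** At 20% dropout with independent people it rejects about 2%, so it starts with slack. With five units of each size per arm it rejects 5.3% at ρ = 0.3 and 7.6% at ρ = 0.5; with all trios, 7.0% and 10.9%. It deals with small counts, not with units.

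**Step 5: a test that respects the units.** A permutation test over whole units rejects about 3–5% with ten units of each size, and about 0.5–3% if everyone is in a trio.

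**The case against.** The strongest reply is that the size of the problem is unknown and may be slight. Joining a cluster is a choice, and the plan expects some people to be randomised singly. With six pairs among 60 people the error stays at about 5–8%. This stands, and is why the range above starts there.

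Dropout also has no hypothesis, power figure or decision rule of its own; the Aim 1 hypothesis concerns symptoms and related psychopathology. The plan will record reasons for dropout and compare them between arms, so a joint exit could come to light. Both points stand and limit the weight of the concern.

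It might be said that section G already covers this, since it applies dummy codes to every analysis. Those codes are for treatment group, not randomisation unit, and a two-way chi-square cannot carry covariates. The latitude given later in the Dropout paragraph to choose a suitable test attaches to comparing the psychopathology and functioning of dropouts, not the dropout percentage.

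Two stronger readings are tempting and not supported:
- A reader might infer that clusters are friends or relatives who will leave as a block. The documents say neither.
- A reader might infer that one trio's departure is enough for significance. At 30 v 30 with no other dropout it is not (p = 0.076).

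**Conclusion.** The concern holds in a limited form. The stated test ignores a unit of randomisation that the same Aim models for its symptom outcomes, and nothing else in the document repairs this. If unit members tend to leave together, the nominal 5% error becomes roughly 5–20% over the assumed mixes and correlations. Where in that range the trial falls depends mainly on how many people enrol in clusters. With all singles or zero correlation the test is sound. These figures leave out any further correlation within the active-arm treatment groups of 5–7.

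A reader might infer that the efficacy result is compromised. It is not: the primary PS-SR-5 analysis models the clusters and does not use this test. This is a minor correction to a secondary comparison.

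**What to change.** In the Dropout paragraph of Specific Aim 1, replace the chi-square test with a permutation test. Keep each randomised unit's members and dropouts together, re-allocate whole units to arms by the trial's own allocation procedure, and compare the observed difference in dropout percent with the resulting distribution. The documents give only the 1:1 ratio and the unit sizes, so the procedure should be stated in enough detail to be repeated.

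Report the difference in dropout percent with an interval clustered on the randomised unit, and give the number of units as well as people who left each arm. State that this interval does not cover correlation within the active-arm treatment groups.

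The cost is a sentence or two in the plan and a few lines of code, using allocation units that the trial must record anyway. The drawback is some loss of sensitivity. With 30 units, 15 per arm, and nobody leaving the other arm, four dropout units all in one arm give p = 0.10 and five give p = 0.042, so at least five are needed. If everyone enrols in trios the test is conservative (about 0.5–3%).

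### The Aim 2 GLMs and the GLM mediation state no adjustment for the units of up to three people randomised together, so their standard errors are too small if members of a unit are alike

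*Combined protocol and SAP*

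**What the plan says.** Section A describes the design as "1:1 randomization, using cluster randomization of one to three individuals". Section D confirms a 1:1 ratio, "allowing for individuals or clusters of up to three individuals being randomized as a unit", and section F sets the size: "we will recruit 30 individuals per treatment group".

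The Specific Aim 1 analysis recognises the consequence. Its reason for choosing mixed models begins: "Because of the presence of clustering (participants in groups, observations over time, and participants in random assignment clusters"). It specifies random intercepts for therapy group and for randomised cluster, the latter only for people who chose to be randomised together.

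Specific Aim 2 uses both GLMs and GLMMs. The GLMMs follow the Aim 1 specification. The GLMs are described separately: "In the GLMs, treatment will predict negative beliefs, connectedness, and forgiveness from baseline to post-treatment (controlling for baseline levels"). Under the Exploratory Hypothesis, the GLM mediation predicts Session 3 mediators from treatment, and follow-up outcomes from the mediator, controlling for treatment and baseline. On inference it says: "Mediation will be tested using the product of coefficients method with bootstrapped standard errors". The resampling unit is not stated.

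Two provisions in section G bear on this. Therapy group in the treatment condition is to be dummy-coded in every analysis. Data are also to be screened for independence of errors, among other assumptions, with respecification if an assumption fails.

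**The concern.** In the Aim 2 GLMs the unit of analysis is the person, while the unit of randomisation may be a pair or a triple. People who ask to be randomised together are likely to be friends or relatives, and may resemble one another on beliefs, connectedness and forgiveness more than strangers do. Those are the Aim 2 outcomes. The treatment effect then varies more from one randomisation to another than a person-level model reports. Intervals come out too narrow, and mediator effects look better established than they are.

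The plan knows of this dependence and models it in one family but not in the other. It does not say which family governs if the two disagree. The effect of treatment on the mediators is a stated hypothesis; only the mediation itself is labelled exploratory.

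**Working it through.** **The plan's own figure.** Section F gives a detectable d = 0.72 at 80% power and alpha .05, with 30 per group and 20% dropout, and applies the same calculation to Aim 2. Using (z_alpha + z_power) × √(2/n):
- 24 per arm, one-sided: (1.645 + 0.842) × √(2/24) = 0.718.
- 30 per arm with no loss, two-sided: (1.960 + 0.842) × √(2/30) = 0.723.
- 24 per arm, two-sided: 0.809, which does not match.

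Sidedness is not stated, and that is a separate matter. What counts here is that both matching versions assume independent participants.

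**Do other provisions reach the randomised units?**
- *Dummy codes.* Their stated purpose is nesting within groups in the treatment condition. They may absorb some correlation when unit members sit in the same therapy group, but they do nothing for units on the waitlist. A code for every group plus a treatment indicator is also rank deficient: with five groups (assumed), there are 7 columns and rank 6.
- *Independence screen.* It names no remedy.
- *GLMM specification.* It carries the unit intercept into the Aim 2 GLMMs only.

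**Size of the effect.** Inputs from the documents: 60 people, units of 1 to 3, 1:1 allocation, and "With a conservative estimated dropout of 20% across conditions". Inputs assumed because the documents do not give them: within-unit ICC of 0.1 to 0.4, the mix of unit sizes, and a baseline–outcome correlation of 0.6.

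Before loss, with units of size m, the design effect is 1 + (Σm²/Σm − 1) × ICC. With 20% random loss, within-unit pairs fall to 0.8² and people to 0.8, so the bracket is multiplied by 0.64/0.8 = 0.8. For equal numbers of sizes 1, 2 and 3, it goes from 140/60 − 1 = 1.33 to 1.07.

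The true standard error is √DE times the reported one. The actual two-sided type I error is approximately 2 × [1 − Φ(1.96/√DE)]. The last column gives simulated rates for a person-level ANCOVA without group dummies. Paired values are for ICC 0.1 and 0.4.

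| Uptake (assumed) | Bracket after loss | DE | √DE | Formula | Simulated |
|---|---|---|---|---|---|
| 30% in units (e.g. 42 singles, 6 pairs, 2 triples) | 0.8 × (84/60 − 1) = 0.32 | 1.032, 1.128 | 1.016, 1.062 | 5.4%, 6.5% | 5.3%, 6.1% |
| Sizes 1, 2, 3 in equal numbers | 0.8 × (140/60 − 1) = 1.07 | 1.107, 1.427 | 1.052, 1.194 | 6.2%, 10.1% | 6.0%, 10.3% |
| All in threes | 0.8 × (180/60 − 1) = 1.60 | 1.160, 1.640 | 1.077, 1.281 | 6.9%, 12.6% | 6.7%, 13.1% |

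Formula and simulation agree closely. At ICC 0 the inflation disappears.

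**Mediation.** Simulated indirect effect with a = b = 0.5 (assumed) and everyone in threes:

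| ICC | True SD of a×b | Person-level bootstrap SE | Unit-level bootstrap SE |
|---|---|---|---|
| 0 | 0.130 | 0.133 | 0.128 |
| 0.10 | 0.152 | 0.136 | 0.137 |
| 0.20 | 0.156 | 0.138 | 0.148 |
| 0.30 | 0.167 | 0.138 | 0.159 |

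At ICC 0.30, resampling persons gives 0.138/0.167 = 83% of the true SD and resampling units gives 0.159/0.167 = 95%. At ICC 0.10 the gain is negligible.

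**The case against.** Much of the case on the other side stands.

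- *A unit-aware Aim 2 analysis is already planned.* A reader might infer that Aim 2 has no cluster-adjusted model. That is wrong: the Aim 2 GLMMs follow Aim 1, carry the unit intercept and also estimate post-treatment levels. The gap is confined to the GLM family and to the lack of a rule on which family governs.
- *The bootstrap is not said to be by person.* A reader might infer that it is, but the plan is silent. What can be said is that a default bootstrap would resample persons.
- *Too-small standard errors are conditional.* They need a positive ICC and enough people randomised in units. Joint randomisation is optional, and at 30% uptake the error stays near nominal.
- *The inflation is easily overstated.* The factor 1 + 1.33 × ICC for sizes 1, 2 and 3 applies before dropout. With the plan's 20% loss it is about 1 + 1.07 × ICC.
- *The stakes are limited.* The primary PTSD analysis is a GLMM with the unit term. The mediation is exploratory and acknowledged to be underpowered. Aim 2 is framed around effect sizes, and ignoring units distorts their intervals rather than the estimates.

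The independence screen is the weakest defence. The dependence follows from the design and is known in advance, and with units this small and few a diagnostic could easily miss it. Low power does not excuse an interval that is too narrow.

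**Conclusion.** The concern holds for the Aim 2 GLMs and the GLM mediation only. As written they make no allowance for the randomised units that the plan models elsewhere, and no other provision supplies one. With ICC between 0.1 and 0.4, the reported standard error should be multiplied by about 1.02 to 1.06 at 30% uptake, and by about 1.08 to 1.28 if everyone is in threes. The corresponding type I error runs from near nominal to about 13%. These figures rest on assumed ICCs and unit mixes, a baseline–outcome correlation of 0.6, 20% random loss and no group dummies. The documents do not support extending the point to the primary outcome, to Aim 1 or to the Aim 2 GLMMs.

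**What to change.** For the Aim 2 pre-post models, do one of the following and state it in the plan:
1. add the randomised-unit term already specified for Aim 1;
2. keep the GLMs, with small-sample cluster-robust (CR2) standard errors by randomised unit, people randomised alone counting as units of one; or
3. name the Aim 2 GLMM as the basis for inference and report the GLM as descriptive.

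For the GLM mediation, state that the bootstrap draws whole randomised units within arm.

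The cost is a few lines of text and a change of resampling unit in the code. The only data needed is the unit identifier, which the GLMMs already require. Intervals become slightly wider, in line with the √DE values above. With few units per arm (ten if everyone is in threes), unit resampling may still fall somewhat short of the true variability, so mediation intervals should be read with that in mind.
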